The trial is designed to have adequate power to test the null hypothesis $H_0: \log(\lambda_1 / \lambda_{2/3}) = 0$ versus the alternative hypothesis $H_a: \log(\lambda_1 / \lambda_{2/3}) \geq 1.3$ for the comparison of overall survival between the remaining experimental arm (arm 2) and the standard arm (arm 1). The power analysis is based on the following assumptions: (1) the 2-year overall survival rate of the remaining experimental arm (arm 2) is 57.3% and that of arm A is 48.5%. Under exponential survival distribution, the median survival for the remaining experimental arm is 29.9 months and for the standard arm is 23 months, or a hazard ratio of 1.3 (λ_1 / λ_2) for the standard arm to the remaining experimental arm; (2) an accrual length of 6 years; (3) 303 eligible patients in the standard arm and 303 eligible patients in the remaining experimental arm; (4) additional follow-up of 2.5 years after the last enrollment; (5) a two-sided significance level of 0.05. Under these assumptions, at the time of final analysis, at least 483 deaths are anticipated under alternative hypotheses for the two remaining comparative arms. Without taking into account the expected minimal loss of power due to interim analyses, the power in detecting the survival improvement for the remaining experimental arm (arm 2) as compared to the standard arm is at least 81.9% using a stratified log-rank test.

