
Secondary Endpoints
 
Esophagitis
	
Hypothesis B: At 12 weeks after the start of XRT, patients in the 45Gy arm will experience worse esophagitis than those in the high dose daily (70Gy) and concomitant boost RT (61.2 Gy) groups.
	
ECOG Acute Esophagitis Scale
 
Difficulty swallowing
	
Dichotomized or ordinal scores/outcomes
 
Chi-square test; Logistic regression; Nonlinear mixed effect or generalized linear model with generalized estimating equations using log or multi-log link.

Psychological state
	
Hypothesis B: At 12 weeks after the start of XRT, patients in the 45Gy arm will report a worse psychological state than those in the high dose daily (70Gy) and concomitant boost RT (61.2 Gy) groups.
	
Hospital Anxiety and Depression Scale (HADS)
	
Continuous scores/outcomes
 
T test; Analysis of covariance; Line mixed effect model or general linear model with generalized estimating equations

Quality-adjusted Life Years (QALY)
	
Hypothesis B: At 12 weeks after the start of XRT, the QALY of those in the 45 Gy will be worse than those in the high dose daily (70Gy) and concomitant
	
EQ-5D
	
Quality adjusted time to event variable/outcome
 
Generalized log rank test for QALY data

	boost RT (61.2 Gy) groups.		
Treatment Inconvenience	Hypothesis C: At 7 weeks after the start of XRT, treatment inconvenience will be greatest for those receiving 70Gy QD in 7 weeks.	Single item developed for the study	Dichotomized or ordinal scores/outcomes Chi-square test; Logistic regression; Nonlinear mixed effect or generalized linear model with generalized estimating equations using log or multi-log link.

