We define swallowing difficulty score as 4 or 5 as “Severe” and scores 1, 2, or 3 as “Moderate.” Similar to the ECOG esophagitis score, with 150 patients in each study arm, we have 80% power to detect a 18% difference of severe swallowing difficulty between the two study arms, assuming 35% swallowing difficulty for arm 1 and 17% in the other arm.

The depression and anxiety scores of HADS are of primary interest. Consider the change score between baseline and 12 weeks after the start of radiation therapy. With 150 in each of the two remaining arms, one has 85% power to detect an effect size of 0.419 s.d. unit on the scale of change score using a two group t-test at a significance level of 0.01.

Quality-adjusted life years (QALY) is calculated as EQ-5D utility score weighted survival time. For the purpose of power calculation, consider a patient with a QALY greater than 12 weeks as “success” and less than 12 weeks as “failure.” With a size of 150 patients having EQ-5D score at baseline and 12 weeks, we have 90% power to detect a 20% difference of 12-week success rate, assuming the 12-week success rate is 65% for arm 1 (45 Gy) and 85% for the remaining experimental arm.

Hypothesis C

The different treatment arms have different dose schedules for different lengths of times, which may impact the satisfaction with treatment due to the inconvenience posed. Patients with an inconvenience rating of 1 or 2 will be defined as “Inconvenient” and those with a rating of 3 or 4 as “Convenient.” If the remaining experimental arm is arm 2 (70 Gy), with 150 patients having inconvenience measure on each arm at baseline and 12 weeks after the start of radiation therapy, a two group continuity corrected Chi-square test at a significance level of 0.05 will have 81% power to detect the 16% difference of the proportion of patients reporting treatment inconvenience between the two remaining study arms, assuming 60% of patients in arm 1 report treatment inconvenience and 76% of patients in arm 2 report inconvenience. If arm 2 is discontinued after 30 patients have been accrued to the main study, with about 150 patients in arm 1 and 15 patients in arm 2 having complete assessment at baseline and 12 weeks, we will have 74% power to detect the 30% difference of the proportion of patients reporting treatment inconvenience between the two remaining study arms, assuming 60% of patients in arm 1 report treatment inconvenience and 90% of patients in arm 2 report inconvenience.

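### The 90% power quoted for quality-adjusted life years is correct arithmetic for 65% versus 85%, but that event and those rates do not fit the plan's own QALY definition and survival assumptions, so the planned QALY test has no valid stated power.

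*Combined protocol and SAP*

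**What the plan says.** Section 15.7 (Power Analysis, Hypothesis B) states that QALY "is calculated as EQ-5D utility score weighted survival time". For power only, it proposes to "consider a patient with a QALY greater than 12 weeks as" a success and anything below as a failure. The calculation uses 150 patients with an EQ-5D at both time points, and its claim reads: "we have 90% power to detect a 20% difference of 12-week success rate, assuming the 12-week success rate is 65% for arm 1". The rate it assumes in the other arm is 85%. No source or utility value is given for either rate. QALY is one of five comparisons in this set, so the Bonferroni level is 0.05/5 = 0.01, and tests are two-sided.

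Four other places bear on this:

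- Section 10.2.3 scales the EQ-5D utility from 0 (worst imaginable health) to 1 (best imaginable health).
- Table 2 in Section 15.7 places the QALY hypothesis at 12 weeks after the start of radiotherapy and names the analysis as "Generalized log rank test for QALY data". The Analytic Methods text in the same section describes it as quality-adjusted overall survival, compared by a published test for quality-adjusted lifetime.
- Section 15.3 assumes exponential survival in which "the median survival for the remaining experimental arm is 29.9 months and for the standard arm is 23 months".
- Section 15.1.1 measures survival from randomization, while Sections 6.2 and 10.2.2 time the quality-of-life visits from the start of radiotherapy.

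**The concern.** A QALY is time multiplied by a weight of at most 1. A success defined as more than 12 quality-adjusted weeks, described as a 12-week rate and computed in patients with a week-12 EQ-5D, looks unattainable if the clock stops at week 12. If the clock runs over all of survival, the plan's own medians of roughly two years make success common in both arms, and an arm 1 rate of 65% looks too low.

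If neither reading yields 65% versus 85%, the 90% describes a comparison the design does not produce. A reader of the results could then take a null QALY finding as evidence against a difference the companion was well powered to detect. Section 15.7 invites that reading when it says that the assumed completion rate secures adequate power for the planned comparisons.

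**Working it through.** **Inputs.** From Section 15.7: 150 per arm, 65% and 85%, two-sided 0.01. From Section 15.3: medians 23 and 29.9 months, exponential. From Section 10.2.3: utility at most 1. Section 15.7 does not restate the QALY level and test; they are taken from the esophagitis comparison in the same set (0.01, continuity-corrected chi-square).

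**1. Reproducing the 90%.** With d = 0.20, the continuity correction gives an effective n of 150 − 2/d + 1/(150d²) = 150 − 10 + 0.17 = 140.2. With a pooled proportion of 0.75:

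z = [0.20√140.2 − 2.576√(2 × 0.75 × 0.25)] / √(0.65 × 0.35 + 0.85 × 0.15) = 1.33, so power is 90.8%.

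Exact binomial power of the corrected test is 91.3%. Without the correction, the normal approximation gives 92.8%.

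**2. QALY counted to week 12, same origin.** The maximum is 1 × 12 = 12 weeks, so the probability of exceeding 12 is 0 in both arms.

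**3. QALY counted over full survival.** At 365.25/12/7 = 4.348 weeks per month, the medians M are 23 × 4.348 = 100.0 and 29.9 × 4.348 = 130.0 weeks. With a constant mean utility u, success means surviving beyond 12/u weeks:

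P(success) = exp(−ln 2 × 12 / (uM)).

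The utilities below are assumptions. Power is exact, continuity corrected, at 0.01 with 150 per arm.

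| Utility, arm 1 / experimental | Success, arm 1 | Success, experimental | Power |
|---|---|---|---|
| 1.0 / 1.0 | 92.0% | 93.8% | 1.2% |
| 0.8 / 0.8 | 90.1% | 92.3% | 1.7% |
| 0.6 / 0.6 | 87.1% | 89.9% | 2.3% |
| 0.5 / 0.5 | 84.7% | 88.0% | 2.7% |
| 0.6 / 0.8 | 87.1% | 92.3% | 10% |
| 0.5 / 0.8 | 84.7% | 92.3% | 25% |
| 0.4 / 0.8 | 81.2% | 92.3% | 55% |
| 0.3 / 0.8 | 75.8% | 92.3% | 90% |

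**4. Utilities implied by 65% and 85%.** Arm 1 survival falls to 65% at −ln(0.65)/ln 2 × 100.0 = 62.2 weeks, so u = 12/62.2 = 0.19. Experimental survival falls to 85% at −ln(0.85)/ln 2 × 130.0 = 30.5 weeks, so u = 12/30.5 = 0.39.

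**5. Patients alive at week 12.** The 150 have a week-12 EQ-5D and so are alive then. Dividing the success rates by S(12), which is 0.920 in arm 1 and 0.938 in the experimental arm, gives at least 92% success in each arm for equal utilities of 0.5 to 1, and power of about 1% or less. The implied utilities fall to 12/(12 + 62.2) = 0.16 and 12/(12 + 30.5) = 0.28. Unequal utilities do better here than in the table: 0.6 versus 0.8 gives 94.6% versus 98.4% and power 10%; 0.5 versus 0.8 gives 92.0% versus 98.4% and 39%; 0.4 versus 0.8 gives 88.3% versus 98.4% and 82%.

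**6. Two-sample mean approximation.** The detectable difference is (2.576 + 0.842 or 1.282) × √(2/n). For n = 150 it is 0.39 SD at 80% power and 0.45 SD at 90%. For n = 188, the eligible number expected per arm in Section 15.7, it is 0.35 and 0.40 SD.

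**The case against.** The strongest reply is that nothing was miscalculated, and that stands. Given 65% and 85%, the 90% is right, so a reader who infers an arithmetic error would be mistaken.

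A reader might also infer that true power is 1-3%. The documents do not support that as a single answer. It requires equal utilities, whereas Hypothesis B expects arm 1 to have worse esophagitis, worse psychological state and lower QALY. Unequal utilities raise power substantially, more so among patients alive at week 12. Reaching about 90% still takes a wide, sustained gap: at u = 0.3, the arm 1 mean must hold for 12/0.3 = 40 weeks. The plan states no such gap.

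Calling the event impossible is strict only under a common origin. If QALY ran from randomization and the visit from the start of radiotherapy, treatment starting up to a week after registration (Section 8.0) and radiotherapy starting at cycle 2 could put that visit at about 13 to 16 weeks. The event would then be possible with a mean utility above 12/13 = 0.92 down to 12/16 = 0.75. The plan neither adopts that reading nor gives the utility distribution it would need. Nor is success near universal over full survival: 85-92% in arm 1 leaves 8-15% failures.

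Finally, the dichotomy was meant only for power, and the planned analysis does not use it. That is true, and it leaves the planned analysis without a power statement of its own.

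**Conclusion.** The point holds as a fault in the event and the assumed rates. Counted to week 12 from a common origin, success has probability zero. Over full survival, the Section 15.3 medians give 65% and 85% only with mean utilities near 0.19 and 0.39. Across the assumed utilities, power for the dichotomy runs from 1-3% (equal, 0.5 to 1) through 10%, 25% and 55% to about 90% at 0.3 versus 0.8. These figures rest on exponential survival and on a utility that is constant over time and the same for every patient in an arm; the documents supply no utilities to check this against.

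The 90% therefore cannot be relied on for the generalized log-rank analysis of quality-adjusted survival. A reader might go further and doubt the companion's size or the main trial's power. The documents do not support that: QALY is one of five comparisons in a set listed as secondary, the other quality-of-life comparisons have their own calculations at 150 per arm, and the overall survival design does not use this figure.

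**What to change.** In Section 15.7, withdraw the 12-week success calculation and its 90% claim. State the QALY time origin and horizon, and make the 12-week time point in Table 2 and the quality-adjusted overall survival in Analytic Methods agree. Then restate power, or the detectable difference, for the planned generalized log-rank type test under explicit utility and survival assumptions, using the number actually analysed.

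If a two-sample mean approximation is quoted instead, label it as one and match it to the analysis set: at 0.01, with 80% and 90% power, 0.39 and 0.45 SD for 150 per arm, or 0.35 and 0.40 SD for 188 per arm.

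The cost is a revision of the statistical text and one power calculation for the planned test. Section 5.6 records that the companion closed to accrual on August 30, 2017 with its target met, so enrolment cannot change, and no new data are needed.

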In the quality of life companion, patients will be assessed by multiple HRQOL (Health-related quality of life) scales at baseline, 3, 5, 7, 12, 26 and 52 weeks (see [Table 1](#) for details). Investigators are interested in evaluating the change of quality of life assessments from baseline to multiple time points during and after treatment and comparing the differences of such changes between treatment regimens. It is expected that patients in arm 1 (45 Gy) experience worse physical and functional well being, worse esophagitis than those in the remaining study arm (arm 2 or 3), and that patients in arm 2 (70 Gy) experience worse treatment inconvenience than those in arm 1 (45 Gy) or arm 3 (61.2 Gy). The HRQOL scores changed from baseline to 12 week are of the primary scientific interest. The size of the HRQOL companion is chosen such that one has adequate power to test three sets of scientific hypotheses as shown in Table 2). The companion will register 415 patients (57%) from the 729 patients consenting to the main treatment study. Of the 415 patients, 394 patients are expected to meet the eligibility criteria. Of the 394 patients on the companion study, 188 patients are expected in each of the two remaining study arms and 18 patients are in the discontinued study arm.

Table 2
Quality of Life Assessment

QoL Endpoint Variable	Hypothesis	Measure	Statistical Analysis

Primary Endpoints Physical Well-being, Functional Well-Being, Lung Cancer physical symptoms
 
FACT Esophageal Eating and Swallowing Subscales
	
Hypothesis A: At 12 weeks after the start of XRT, patients in the 45Gy arm will report worse physical symptoms and functioning than those in the high dose daily (70Gy) and concomitant boost RT (61.2 Gy) groups.
	
FACT-L (TOI)
 
FACT Esophageal Eating and Swallowing Subscales
	
Continuous scores/outcomes
 
T test; Analysis of covariance; Linear mixed effect model or general linear model with generalized estimating equations

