The following assumptions are made in the power calculations: (1) Based on the literature and previous CALGB studies, we expect that at least 80% of eligible patients who register to the companion will complete the HRQOL assessments at both baseline and 12 weeks after the start of radiation therapy. That is, of the 394 eligible patients on the companion study, 150 patients in the two remaining study arms and 15 in the discontinued study arm will have complete HRQOL assessments at both baseline and 12 weeks after the start of radiation therapy; (2) Within each set of hypothesis (A, B, C), Type I error will be controlled at the level of 0.05. The Bonferroni method is used to address the issue of multiple comparisons for simplicity and reasonable performance with a small number of comparisons; and (3) Two-sided tests will be used.

Hypothesis A

Three planned comparisons will be made to address Hypothesis A. The total TOI score from FACT TOI, the eating score and the swallowing score will be calculated from the FACT-Esophagus Subscale. The change scores between baseline and 12 weeks after the start of radiation therapy are of interest. A size of 150 patients with complete assessments at baseline and 12 weeks after the start of radiation therapy in each of the two remaining arms will have 85% power to detect an effect size of 0.397 s.d. unit on the scale of change score using a two group t-test at a significance level of 0.0167 (0.05/3). The effect size of 0.397 s.d. is usually associated with a moderate effect in quality of life literature.

Hypothesis B

Five comparisons will be made to address this hypothesis - ECOG esophagitis score (severe/ ≥ 7 vs moderate/ < 7), difficulty swallowing (severe/ ≥ 4 vs. moderate/ < 4), HADS depression score, HADS anxiety score, and quality-adjusted life year (QALY).

The ECOG esophagitis score ranges from 0 to 12 points. We will define patients with scores of ≥ 7 as “Severe” and score < 7 as “Moderate.” With 150 patients in each remaining arm with complete assessments at baseline and 12 weeks after the start of radiation therapy, a two group continuity corrected Chi-square test at a 2-sided significance level of 0.01 (0.05/5) will have 80% power to detect the 18% difference of the proportions of patients with severe symptoms between the two remaining study arms, assuming 35% of patients in arm 1 report severe symptoms and 17% in the other remaining arm (odds ratio of 2.625).

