Analytic Methods:

For continuous HRQOL (Health-Related Quality of Life) scores, including Physical Well-Being, Functional Well-Being, Lung Cancer Physical Symptoms subscale scores from the FACT-TOI, Eating and Swallowing subscale scores from the FACT-Esophagus Subscale, and depression and anxiety subscale scores from HADS, two-group t test and analysis of covariance will be the primary method used to analyze and test the planned comparisons for the change scores from baseline to 12 weeks after the start of radiation therapy with and without adjusting for other prognostic factors. In analysis of covariance, in addition to study arm, significant baseline prognostic factors will be included in the model to adjust for confounding effects. These planned tests results will be reported at the significance level designated in the section of power analysis. Similar exploratory univariate analyses will be conducted for the change score from baseline to other assessment points at 3, 5, 7, 26, and 52 weeks after the start of radiation therapy. Multivariate analyses for evaluating the trend of HRQOL scores varying over time will be conducted using a linear mixed effect model and linear model with generalized estimating equation (GEE) with all valid measures from multiple time points included in the analysis.

For binary dichotomized endpoints, such as ECOG esophagitis severity (severe/ ≥ 7 vs moderate/ < 7), difficulty swallowing (severe/ ≥ 4 vs. moderate/ < 4) and ordinal endpoints, such as treatment inconvenience (inconvenient/ ≤ 2 yes vs. convenient/ ≥ 3), Chi-square test and generalized linear model with a logit or multi-logit link will be used to test the planned comparisons. In regression analysis, baseline prognostic factors besides study arm will be included. Again, these planned tests will be reported at the significance level as designated in the section of power analysis. Similar multivariate analyses for evaluating the trend of HRQOL scores varying over time will be conducted using a nonlinear mixed effect model and generalized linear model with generalized estimating equation (GEE) with all valid measures from multiple time points included, in which logit link for dichotomized scores and multi-logit link for ordinal scores will be specified. In the analysis of ordinal scores, proportional odds assumptions will be tested.

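### For the continuous QoL scores the plan calls two unranked analyses primary and fixes no covariates; it should name one ANCOVA that includes the baseline score

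*Combined protocol and SAP*

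**What the plan says.** Section 15.7, Analytic Methods, covers the continuous scores in one paragraph. It says that "two-group t test and analysis of covariance will be the primary method used to analyze and test the planned comparisons for the change scores". The interval is baseline to week 12, and both adjusted and unadjusted results are planned. For the ANCOVA, "in addition to study arm, significant baseline prognostic factors will be included in the model to adjust for confounding effects". No list of candidate factors, threshold or selection procedure follows, and the baseline value of the score under test is not named. On the level, "These planned tests results will be reported at the significance level designated in the section of power analysis".

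The Power Analysis part of the same section promises: "Within each set of hypothesis (A, B, C), Type I error will be controlled at the level of 0.05". It does this by Bonferroni over endpoints, 0.05/3 for Hypothesis A (TOI, eating, swallowing) and 0.05/5 for Hypothesis B (which includes the two HADS scores). Its calculations for continuous scores use a two-group t test on the change score.

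Table 2 in section 15.7 lists for the primary QoL endpoints "T test; Analysis of covariance; Linear mixed effect model or general linear model with generalized estimating equations", with no order of precedence. The Analytic Methods text assigns the mixed model and GEE to trends over time, so two candidates remain for the week-12 comparison.

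**The concern.** There are three linked gaps. First, two tests share the primary label and nothing says which one decides, while the whole error budget is spent on the number of endpoints. Second, the adjusted model is not defined until the data are in, so two analysts following the plan could report different primary p-values. The reason given, confounding, does not call for data-driven selection in a randomised comparison. Third, the one covariate most likely to sharpen each comparison, the baseline value of the same score, is already collected (section 6.2) but not fixed in the model.

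Section 15.7 puts its primary scientific interest in the changes from baseline to week 12. Section 15.4 says that with roughly equal survival the recommendation might turn on toxicity or convenience. The QoL comparisons could then carry real weight, so their decision rule should be unambiguous.

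**Working it through.** **Inputs from section 15.7:** 150 patients per arm with both assessments; two-sided tests; effect 0.397 SD of the change score at 0.05/3 (Hypothesis A); effect 0.419 SD at 0.01 (HADS); 85% power for each. **Not in the documents, so assumed with a range:** the correlation ρ between baseline and week 12, and the ratio k of the week-12 SD to the baseline SD.

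**1. The plan's own figure.** The noncentrality is d√(n/2), with 298 degrees of freedom.
- Hypothesis A: 0.397 × √75 = 3.438, power 84.8%.
- HADS: 0.419 × √75 = 3.629, power 84.9%.

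The stated 85% reproduces.

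**2. Efficiency of baseline adjustment.** In units of the baseline variance, the change score has variance 1 + k² − 2ρk, and the baseline-adjusted ANCOVA has residual variance k²(1 − ρ²). Their difference is (1 − ρk)², which is never negative. Apart from one degree of freedom, adjustment therefore cannot be less efficient in large samples. It gains nothing when the within-arm slope ρk equals 1. The variance ratio is f = k²(1 − ρ²)/(1 + k² − 2ρk), which is (1 + ρ)/2 when k = 1. Under randomisation both methods estimate the same raw difference, so the standardised effect becomes d/√f.

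| ρ | f, k = 1 | 0.397/√f | Power, Hyp. A | Power, HADS | f, k = 1.25 | Power, Hyp. A, k = 1.25 |
|---|---|---|---|---|---|---|
| 0.3 | 0.65 | 0.492 | 96.8% | 97.1% | 0.785 | 92.9% |
| 0.5 | 0.75 | 0.458 | 94.0% | 94.4% | 0.893 | 89.0% |
| 0.7 | 0.85 | 0.431 | 90.6% | 91.0% | 0.981 | 85.6% |
| 0.9 | 0.95 | 0.407 | 86.8% | 87.0% | 0.950 | 86.8% |

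With k = 0.8, power for Hypothesis A is 97% to 99% for ρ from 0.3 to 0.7. With ρ = 0.7 and k = 1/0.7 ≈ 1.43, the slope is 1 and power is 84.8% by either method. At ρ = 0.5 and equal SDs, 85% power would need about 0.75 × 150 ≈ 112 patients per arm.

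**3. Type I error if either p-value may be claimed.** Null simulations with 150 per arm at level 0.05/3 gave these results for the t test or a baseline-adjusted ANCOVA (equal SDs, 10,000 runs each):
- ρ = 0.3: 0.027
- ρ = 0.5: 0.024
- ρ = 0.7: 0.024

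The bivariate normal calculation, with correlation √((1 + ρ)/2) between the two statistics, gives 0.027, 0.026 and 0.024.

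For the t test or an ANCOVA with covariates kept at p < 0.05 (six assumed independent factors, joint R² 0.05, 0.10 and 0.20; 100,000 runs each), the results were 0.022, 0.023 and 0.025.

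The Bonferroni bound over three endpoints then lies between 3 × 0.022 = 0.066 and 3 × 0.027 = 0.081.

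**4. Type I error from covariate selection alone.** In the same 100,000-run simulations, the selected-covariate ANCOVA on its own rejected 0.019, 0.018 and 0.017 of the time, against a nominal 0.0167. Selection by association with the outcome leaves the level close to nominal.

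**The case against.** The strongest reply is that the t test is implicitly the confirmatory test. The tests are to be reported at the levels in the power section, and for continuous scores that section attaches levels only to a two-group t test. On this reading the ANCOVA is just the adjusted version, and no error is spent twice. That is a fair reading and probably a common one. But the power section only sizes the study, and the analysis paragraph gives the primary label to both methods. No passage says that either p-value may be claimed; equally, none says that only one may.

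A second reply is that the baseline score could enter as a significant factor. It could: at ρ = 0.5 and equal SDs its correlation with the change is −0.5, and with 300 patients it would almost always be kept. The plan neither includes it nor lists it as a candidate, however.

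A reader might also infer three stronger things that the documents do not support:
- **The companion is underpowered.** It is not; the t test meets its stated 85%. Any loss is relative to a better model.
- **Selecting covariates by significance breaks the 0.0167 and 0.01 levels.** For selection by association with the outcome, step 4 shows no material inflation at 0.0167. Other rules, such as selecting on arm imbalance or on the arm p-value, were not tested, and the plan does not say which it means.
- **ANCOVA gains whenever the correlation is below 1.** That needs equal SDs, and step 2 gives a counterexample.

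**Conclusion.** The point holds as an ambiguity in the decision rule together with a missed, nearly costless gain. It does not show a wrong sample size.

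The type I consequence is conditional. If either result counts, the per-endpoint error is about 0.02 to 0.03 instead of 0.0167, and the promised 0.05 for the hypothesis set is no longer guaranteed. The 0.066 to 0.081 range is a bound; with strongly correlated endpoints the actual error would be lower.

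The power gain for Hypothesis A is about 2 to 12 percentage points with equal SDs and ρ from 0.9 to 0.3. It is smaller if the week-12 SD is moderately larger than the baseline SD, larger if it is smaller, and nil at a slope of 1. These figures rest on assumed correlations, SD ratios and covariate strengths.

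The scope is the five continuous scores of an optional companion study, of which HADS is a secondary QoL endpoint. The overall survival analysis is untouched.

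**What to change.** In section 15.7, Analytic Methods and Table 2:
- Name one primary analysis for each continuous score: an ANCOVA of the week-12 score (or, equivalently for the arm effect, the change) on arm, the baseline value of the same score and a short prespecified list of randomisation factors from section 15.2.
- Remove statistical significance as the rule for choosing covariates.
- Label the unadjusted change-score t test supportive, and state that only the ANCOVA p-value is compared with 0.0167 or 0.01.

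No new data are needed. A change score already requires both assessments, so adding the baseline score excludes no further patient. The sample size can stand, because in large samples the adjusted analysis is at least as efficient as the test used for sizing.

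The one real cost is procedural. Section 5.6 closed the companion to accrual on August 30, 2017, and section 6.1 carries changes dated March and April 2018, so week-12 collection should be essentially over. The change should therefore be dated and documented by people who have not seen QoL results by arm.
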